5.4.2. Additional considerations

For each and all *N. meningitidis* serogroup B test strain (M14459, M07-0241084, 96217 and NZ98/254) and each of the serogroups A, C, W and Y, the percentage of subjects with hSBA titers \geq lower limit of quantitation (LLOQ) and the corresponding exact two-sided 95% CIs based on Clopper-Pearson method will be calculated [Clopper, 1934] for each study group at baseline and at one month after the 1st vaccination and at one month after the 2nd vaccination, for serogroup B test strains, and at one month after (study) vaccination of MenACWY, for serogroups A, C, W and Y.

The hSBA titers/ELISA concentrations at each blood draw visit for each study group will be logarithmically transformed (base10) to fulfil the normal distribution assumption. For each *N. meningitidis* serogroup B test strain (M14459, M07-0241084, 96217 and NZ98/254) and each of the serogroups A, C, W and Y, the GMTs/GMCs and GMRs (compared to baseline) will be calculated, with their associated two-sided 95% CIs, by

exponentiating the corresponding log-transformed means and within-subject mean difference, respectively and their 95% CIs.

The ratio of GMTs between the Group MenB+MenACWY versus Group MenB at one month after the first and the second vaccination, and the corresponding CI will be constructed by exponentiating the mean difference and the confidence limits in log10 (titer), using ANOVA with study centre included as an independent variable.

The ratio of GMTs/GMCs between the Group MenB+MenACWY versus Group MenACWY at one month after the (study) vaccination of MenACWY, and the corresponding CI will be constructed the same way, by exponentiating the mean difference and the confidence limits in log10 (titer/concentration), using ANOVA with study centre included as an independent variable.

Summary tables will show adjusted GMTs/GMCs and adjusted ratios of GMTs/GMCs for each vaccine group. To incorporate possible baseline imbalance among the vaccine groups, an analysis of covariance (ANCOVA) might be performed that incorporate baseline titers/concentrations along with study group and center as factors in the model.

The following SAS code will be used for the ANOVA model:

```
PROC GLM data = dataset;
  class trt center;
  model Ab_post = trt center;
  lsmeans trt / stderr cl tdiff pdiff;
  estimate 'Group A vs. Group B' trt 1 -1;
run;
```

where Ab_post represents the log-transformed antibody value of the immunogenicity variable at a given post baseline timepoint, trt indicates the vaccine group, and center the site.

The following SAS code will be used for the ANCOVA model:

```
PROC GLM data = dataset;
  class trt center Ab_pre;
  model Ab_post = trt center Ab_pre;
  lsmeans trt / stderr cl tdiff pdiff;
  estimate 'Group A vs. Group B' trt 1 -1;
run;
```

where Ab_post represents the log-transformed antibody value of the immunogenicity variable at a given post baseline timepoint, trt indicates the vaccine group, center the site, and Ab_pre the log-transformed antibody baseline value of the immunogenicity variable.

If the statistical model does not converge due to the factor “centre”, merging some centres or including instead “country” in the model will be considered.

For each *N. meningitidis* serogroup B test strain (M14459, M07-0241084, 96217 and NZ98/254) and each of the serogroups A, C, W and Y, the percentages of subjects with fourfold increase in hSBA titers, and the corresponding exact two-sided 95% CIs based on the Clopper-Pearson method [[Clopper, 1934](#)] against these strains will be calculated

for each study group at one month after the 1st vaccination and one month after the 2nd vaccination, for serogroup B test strains, and at one month after (study) vaccination of MenACWY, for serogroups A, C, W and Y. The CIs for the rate difference between groups will be constructed using the method of Miettinen and Nurminen [[Miettinen](#), 1985].

The percentage of subjects with fourfold increase in hSBA titers one month after the 1st and one month after the 2nd vaccination, for serogroup B test strains, and one month after (study) vaccination, for serogroups A, C, W and Y, relative to baseline is defined as:

- If the baseline titer is <limit of detection (LOD), then post-vaccination titer should be ≥ 4 x LOD or \geq LLOQ, whichever is greater
- If the baseline titer is \geq LOD but <LLOQ, then post-vaccination titer should be ≥ 4 x LLOQ
- If the baseline titer is \geq LLOQ, then post-vaccination titer should be ≥ 4 x the baseline titer

Summary tables will show unadjusted percentages and unadjusted “between-group” differences.

The following table contains the LOD and LLOQ values to be used.

Table 5 LOD, LLOQ and ULOQ values

Serogroups / B strains	LOD*	LLOQ*	ULOQ*
A	5	12	4295
C	4	8	54828
W	4	8	10057
Y	4	10	7624
M14459	4	5	Not defined
96217	6	14	Not defined
NZ298/254	4	6	Not defined
M13520	4	6	Not defined

*Strain, assay cut-off(s) and unit(s) might be subject to change during the course of the study (e.g., in case of requalification, revalidation or standardization). In this case, this will be documented either in a protocol amendment or in the clinical report.

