5. STUDY DESIGN

5.1. Scientific rationale for study design

The purpose of this study is to demonstrate the non-inferiority of the antibody response in terms of Human Serum Bactericidal Assay (hSBA) using human complement GMTs against *N. meningitidis* test strains indicative of serogroups A, C, W, Y, and B, after concomitant rMenB+OMV NZ and MenACWY vaccine administration to either vaccine alone in healthy subjects 16-18 years of age.

The selection of the study population is based on ACIP recommendations for use of meningococcal vaccines [ACIP, 2011]. Routine administration of a MenACWY vaccine for all persons aged 11 through 18 years is recommended. A single dose of vaccine should be administered at 11 or 12 years of age, and a booster dose should be administered at 16 years of age. Adolescents who receive their first dose at 13 through 15 years of age should receive a booster dose at 16 through 18 years of age. In Europe, *Menveo* has been approved by EMA for active immunization of children (from 2 years of age), adolescents and adults at risk of exposure to *N. meningitidis* groups A, C, W and Y,

to prevent invasive disease. The use of this vaccine should be in accordance with official recommendations.

To be eligible for this study design, all subjects must have received a previous vaccination with a quadrivalent meningococcal conjugate vaccine (MenACWY; *Menveo* or *Menactra*) at least 4 years prior to study start. The available data support interchangeability of the 2 licensed meningococcal conjugate vaccines [ACIP, 2013]. Consequently, a booster dose of *Menveo* can be administered, regardless of the vaccine brand used for the previous dose.

[figure not shown]
Data collected from this study may support the concomitant use of rMenB+OMV NZ and MenACWY in healthy subjects 16-18 years of age.

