10. STATISTICAL CONSIDERATIONS

10.1. Sample size determination

The target sample size is 750 subjects evaluable for immunogenicity (250 subjects per study group). Evaluable subjects mean all subjects included in the set for the primary statistical analysis defined in Section 10.2) Considering that approximately 20% of the enrolled subjects might withdraw or not be evaluable for immunogenicity, the target sample size to be enrolled is 945 subjects (315 subjects per study group). These sample sizes were calculated based on the standard deviations from corresponding treatments in the mentioned studies, the non-inferiority margin of 0.5 and the expected ratio GMR of the GMTs (or GMCs) of 0.9.

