10.1.2. Sample size calculation

For the immune response to rMenB+OMV NZ, sample size calculations are based on hSBA titer data from the GSK V102_03 and V72_41 studies and for the immune response to MenACWY, data from GSK V59P13E1 study and V102_02 study (ELISA GMCs) is used.

Sample size/power calculations are based on specific fixed values for the

- non-inferiority margin,
- standard deviations of (the distributions of) the logarithmically transformed (base of 10) hSBA titers for the strains M14459, 96217, NZ98/254 and M07-0241084.
- standard deviations of (the distributions of) the logarithmically transformed (base of 10) hSBA titers for the serogroups A, C, W and Y,
- ratios of the GMTs medians of (the distribution of) the hSBA titers for strains M14459, 96217, NZ98/254 and M07-0241084 when rMenB+OMV NZ is administered with MenACWY versus when rMenB+OMV NZ is administered alone (one ratio per strain),
- ratios of the GMTs/GMCs of (the distribution of) the hSBA titers for the serogroups A, C, W and Y when MenACWY is administered with rMenB+OMV NZ vs when MenACWY is administered alone (one ratio per serogroup).

Standard Deviations for hSBA Titer:

In [Table 19](#) the standard deviations are listed that were used in the power calculation, along with the 80% upper limit of the confidence interval (CI) for standard deviation.

For the primary objective 1, hypothesis 1, testing of rMenB+OMV NZ when given concomitantly with MenACWY to rMenB+OMV NZ given alone, test of treatment Group MenB+MenACWY versus treatment Group MenB, the standard deviations from studies V102_03 and V72_41 were used.

For the primary objective 2, hypothesis 2, testing of MenACWY when given concomitantly with rMenB+OMV NZ to MenACWY given alone, test of treatment Group MenB+MenACWY versus treatment Group MenACWY, the standard deviations from study V59P13E1 GrIV_V were used.

For the secondary objective, hypothesis 3, testing of MenACWY when given concomitantly with rMenB+OMV NZ to MenACWY given alone based on ELISA GMCs, test of treatment Group MenB+MenACWY versus treatment Group MenACWY, the standard deviations from study V102_02 were used.

Table 19 Observed SDs with the Upper Limits of the Two-Sided 80% CI for the Logarithmically (base of 10) Transformed hSBA Titers

Hypothesis	study	strain	sd	N	alpha	df	Est_sd
1	V102_03	M14459	0.65413	92	0.2	91	0.72443
1	V72_41	96217	0.25408	30	0.2	29	0.30774
1	V102_03	NZ98/254	0.56100	92	0.2	91	0.62129

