In summary to have an overall power of 90% or more, the minimum sample size need to be N=250 subjects per group. To account for a 20% drop out rate, N=315 subjects per group need to be enrolled. For the study, with 3 treatment groups, N=945 subjects need to be enrolled to have 750 eligible subjects.

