6. ANALYSIS INTERPRETATION

The primary objective is divided in three primary endpoints. The first one regards safety and will be only descriptive. The two other endpoints will be achieved if non-inferiority is demonstrated. Non-inferiority is demonstrated if for each of the four serogroups A, C, W and Y (the four serogroup B test strains: M14459, 96217, NZ98/254 and M07-0241084), the lower limit of the 2-sided 95% confidence interval of the between-group ratio of hSBA GMTs is >0.5 for group MenB+MenACWY versus group MenACWY (for group MenB+MenACWY versus group MenB).

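### The ANOVA that decides the eight hSBA co-primaries omits the Visit 1 titre already assayed, and the baseline-adjusted ANCOVA is left optional with no trigger and no stated role

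*SAP*

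**What the plan says.** - **Success rule.** SAP section 6 requires, for every strain and serogroup, that "the lower limit of the 2-sided 95% confidence interval of the between-group ratio of hSBA GMTs is >0.5". It names no model. Protocol 10.3.3 names none either.
- **Model.** SAP 5.4.2 states that the ratios and intervals for both primary comparisons will be obtained "using ANOVA with study centre included as an independent variable". The code contains treatment and centre only.
- **Optional model.** The same section adds, with possible baseline imbalance as the reason, that "an analysis of covariance (ANCOVA) might be performed that incorporate baseline titers/concentrations". It does not say what counts as imbalance, when the decision is taken, whether the result is supportive, or what happens if the two models disagree. By contrast, SAP 5.4.1.1 explicitly calls the Full Analysis Set analysis supportive.
- **ANCOVA code.** The baseline variable (Ab_pre) is listed in the CLASS statement, so each distinct baseline titre would be fitted as a category.
- **Second specification.** SAP 10.1.5.3 describes an ANOVA with three groups and a country effect, also without baseline. SAP 5.4.2 contrasts two groups and uses centre.
- **Data available.** Protocol Table 14 lists Visit 1 hSBA for all eight co-primary antigens in both arms of each comparison. It lists no Visit 1 ELISA.
- **Population.** Protocol 5.1 says that "all subjects must have received a previous vaccination with a quadrivalent meningococcal conjugate vaccine". Protocol 6.2.2 excludes prior group B meningococcal vaccination.

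**The concern.** A pre-vaccination titre that predicts the post-vaccination titre removes residual variance and corrects chance baseline differences, at no cost in subjects or samples. That relation is plausible for A, C, W and Y, because all subjects were primed at least 4 years earlier. Allocation is minimised on centre only (Protocol 7.2.2.2.1), so baseline titre is not balanced by design. Leaving it out gives away precision on the confirmatory tests.

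The second issue is the unlabelled optional model. If both models are run, each co-primary has two intervals, and the SAP does not say in terms that the ANCOVA cannot bear on the conclusion.

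**Working it through.** **Inputs.** Protocol 10.1 gives "the non-inferiority margin of 0.5 and the expected ratio GMR of the GMTs (or GMCs) of 0.9". Protocol 10.1.2 lists the observed SDs "along with the 80% upper limit of the confidence interval (CI) for standard deviation"; the upper limits (Table 19, log10 scale) drive the power tables. For MenA, C, W and Y they are 0.50866, 0.59455, 0.62875 and 0.65075. Evaluable n is 250 per group ("the minimum sample size need to be N=250 subjects per group"). The test is one-sided at 0.025.

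**Reproducing the plan.** SE = SD × √(2/n). Non-centrality = log10(R/0.5)/SE, with df = 2n − 2 = 498. At R = 0.9, log10(0.9/0.5) = 0.25527. For MenY, SE = 0.65075 × √(2/250) = 0.0582 and non-centrality = 0.25527/0.0582 = 4.39, giving 99.22%. MenA, C and W give 99.99%, 99.77% and 99.49%. The product of the unrounded values is 98.47%, as in Table 21. The MenB product is 96.81%, as in Table 20. The eight primary tests together have 0.9681 × 0.9847 = 95.33%. The stated power therefore rests on an analysis without baseline.

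**Adding a continuous baseline.** Residual SD becomes SD × √(1 − rho²). The documents give no rho, so 0.1, 0.3 and 0.5 are assumed. At R = 0.75, log10(0.75/0.5) = 0.17609.

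| rho | CI width factor √(1 − rho²) | All four A/C/W/Y, R = 0.9 | All four A/C/W/Y, R = 0.75 | Eight primaries, R = 0.9, same rho for all | Eight primaries, R = 0.9, rho for A/C/W/Y only |
|---|---|---|---|---|---|
| 0 (ANOVA) | 1.000 | 98.47% | 66.4% | 95.33% | 95.33% |
| 0.1 | 0.995 | 98.57% | 67.2% | 95.58% | 95.42% |
| 0.3 | 0.954 | 99.19% | 73.6% | 97.29% | 96.03% |
| 0.5 | 0.866 | 99.83% | 85.7% | 99.26% | 96.64% |

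The products treat the antigens as independent, as the protocol does. The 0.75 column applies that ratio to all four serogroups at once. With the observed SDs in Table 19 instead of the upper limits, unadjusted power at 0.75 is 79%.

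**Chance imbalance.** A baseline difference of 1.96 standard errors moves the log10 ratio by rho × 1.96 × SE. For MenY, 1.96 × 0.0582 = 0.114. An adverse imbalance then multiplies the ratio by 10^(−0.114 × rho), which is 0.97, 0.92 and 0.88 for rho 0.1, 0.3 and 0.5.

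**Reporting the better of two models.** At the margin each model alone rejects 2.5% of the time, and the two test statistics have correlation √(1 − rho²). The chance that at least one passes is 2 × 0.025 − P(both pass), which is 2.7%, 3.2% and 3.7% for rho 0.1, 0.3 and 0.5. Simulation with 2,000,000 draws per rho gives the same values. This applies to one antigen sitting exactly at the margin.

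**The case against.** The strongest reply is that the deciding model is already named. The ANOVA is stated as what will be done, with code that will be used, and only the ANCOVA is conditional. A reader might infer that the SAP lets the sponsor pick the deciding interval after seeing the data. The documents do not say this: nothing allows the ANCOVA to replace the ANOVA. What remains is a missing label on the second model.

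A reader might also infer that the unadjusted test is wrong or the trial underpowered. Neither follows. The ANOVA holds its alpha and matches the sample-size basis, and its interval already allows for chance baseline differences. Baseline is also used elsewhere, in the secondary GMRs and fourfold-rise endpoints.

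The prognostic argument is stronger for four of the eight co-primaries. Priming concerns A, C, W and Y; for the B strains, prior MenB vaccination is excluded, so a useful baseline relation is less certain. The size of the gain depends on an assumed rho and is small at the planned ratio. All of this stands and limits the point. It does not remove the case for using a covariate already in hand, or for stating each model's role.

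**Conclusion.** The point holds as a worthwhile improvement, not as a flaw in validity. Under assumed rho of 0.1 to 0.5, all-four MenACWY power gains 0.1 to 1.4 percentage points at the planned ratio of 0.9. The gain is material only if the true ratio is well below plan: at 0.75, with the upper-limit SDs, power goes from 66% to 67-86%. The benefit is more secure for A/C/W/Y than for the B strains.

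The error figure of 2.7-3.7% requires someone to report whichever model is more favourable. It should not be read as the trial's type I error. All eight comparisons must pass, so the effect on the overall claim is at most that size. Correcting the roles of the two models is justified whatever rho turns out to be.

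**What to change.** Before unblinding, amend the SAP as follows.

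1. In 5.4.2, name one deciding model for the eight hSBA co-primaries: log10 post-vaccination titre on group, centre and continuous log10 Visit 1 titre of the same antigen. Label the ANOVA without baseline supportive and delete the conditional wording about the ANCOVA.
2. Take Ab_pre out of the CLASS statement so that it is fitted as a continuous covariate.
3. Reconcile 10.1.5.3 (three groups, country) with 5.4.2 (two groups, centre).
4. State how subjects with a missing Visit 1 titre are kept, for example mean imputation plus a missing indicator, for the covariate only. SAP 10.1.2.2 does not replace missing laboratory results, so this must be written as an explicit exception. Otherwise the ANCOVA drops these subjects, although the missing-serology exclusion in SAP Table 4 concerns post-vaccination results only.
5. Limit the adjustment to hSBA, because no Visit 1 ELISA is planned.

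The cost is edits to three SAP sections and one block of code. No new samples or subjects are needed. If the sponsor prefers to keep the ANOVA as deciding, saying so and labelling the ANCOVA supportive closes the question of roles but forgoes the precision.

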6.2.2. Prior/Concomitant therapy

- Use of any investigational or non-registered product (drug, vaccine or medical device) other than the study vaccine(s) during the period starting 30 days before the informed consent or planned use during the study period.
- Administration of immunoglobulins and/or any blood products or plasma derivatives during the period starting 180 days before the informed consent or planned administration during the study period.
- Previous vaccination with any group B meningococcal vaccine at any time prior to informed consent and assent as applicable (according to the subject's age).
- Previous vaccination with two doses of quadrivalent meningococcal conjugate vaccine (MenACWY, *Menvac*, *Menactra* or *MenQuadfi*).

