10.1.3.9. Geometric mean titres (GMTs) and concentrations (GMCs)

Geometric Mean Titre (GMT) or Concentration (GMC) calculations are performed by taking the inverse logarithm of the mean of the log titre or concentration transformations. Antibody titres or concentrations below the cut-off of the assay will be given an arbitrary value of half the cut-off of the assay for the purpose of GMT/GMC calculation. The cut-off value is defined by the laboratory before the analysis and is described in the protocol.

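### The SAP's optional ANCOVA code declares the continuous log10 baseline titre as a CLASS factor, which distorts that model's adjusted GMTs and can cost precision; the deciding centre ANOVA is coded correctly

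*SAP*

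**What the plan says.** SAP Section 5.4.2 builds the between-group GMT and GMC ratios by "using ANOVA with study centre included as an independent variable". That code puts only treatment and centre in CLASS. The section then announces that "Summary tables will show adjusted GMTs/GMCs and adjusted ratios of GMTs/GMCs for each vaccine group", and adds that, for possible baseline imbalance, "an analysis of covariance (ANCOVA) might be performed".

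The ANCOVA code, introduced as the code to be used for that model, has the CLASS statement "class trt center Ab_pre". The line beneath it defines "Ab_pre the log-transformed antibody baseline value of the immunogenicity variable". Its LSMEANS statement is "lsmeans trt / stderr cl tdiff pdiff", with no observed-margins option. The prose also calls baseline one of the factors in the model, so it would not alert a programmer to the slip.

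Two other rules bear on the result:

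- SAP Section 10.1.3.9: a value below the cut-off "will be given an arbitrary value of half the cut-off of the assay", so all such subjects share one baseline value.
- Protocol Section 6.2.2 excludes "Previous vaccination with any group B meningococcal vaccine at any time prior to informed consent", which makes many low baselines plausible for the B strains. Protocol Section 6.1 requires a previous MenACWY dose, so higher baselines are plausible for A, C, W and Y.

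Separately, SAP annex 10.1.5.3 prescribes an ANOVA with three groups and country for the GMC ratio and adjusted GMT. Section 5.4.2 uses centre, with country only as a fallback if the model does not converge. The annex rules are to be applied along with Section 9, whose method subsection is NA. Nothing says which text prevails.

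**The concern.** An ANCOVA for baseline imbalance should estimate one slope on log10 baseline and compare the arms at a common baseline. With Ab_pre in CLASS the model has no slope. Each distinct titre becomes its own level, and default LSMEANS averages over levels instead of over subjects. A titre held by one subject then weighs as much as the below-cut-off level, which may hold most of the arm. Subjects whose baseline titre is unique add nothing to the treatment contrast.

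This is the only baseline-adjusted analysis of the GMT ratios in the SAP. If baseline imbalance prompts it and it is run as written, its adjusted GMTs would describe a population tilted towards rare high baselines, and its confidence interval could be needlessly wide.

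**Working it through.** **1. The plan's own figure.** With δ = log10(0.9) − log10(0.5) = 0.2553, SD 0.72443 for M14459 (Protocol Table 19) and 250 per group, the standard error is 0.72443 × √(2/250) = 0.0648. The two-sample noncentral t at one-sided 0.025 gives 97.57%, as in Table 20. Overall, 0.9681 × 0.9847 × 0.9465 = 0.9023, as in Table 23. These figures use a two-group comparison with no baseline term, so the coding slip does not touch them.

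**2. Inputs not in the documents.** Baseline GMT, baseline SD, correlation of baseline with post-vaccination titre, number of centres and titre granularity are all assumed. So is reading the cut-off as the LLOQ, because Section 10.1.3.9 does not say whether LOD or LLOQ is meant.

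**3. Effect of equal level weights, by hand.** Take log10 baseline normal with mean log10 3 = 0.477 and SD 0.55, cut-off 8, and two-fold titres.

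| Level | Share of subjects | Mean log10 baseline in level |
|---|---|---|
| below 8 | 78.1% | 0.269 |
| 8 to <16 | 12.6% | 1.039 |
| 16 to <32 | 6.2% | 1.333 |
| 32 to <64 | 2.3% | 1.627 |
| 64 and over | 0.8% | 1.988 |

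- The subject-weighted mean is 0.477. The equal-weight mean is (0.269 + 1.039 + 1.333 + 1.627 + 1.988)/5 = 1.251, a difference of 0.774.
- The slope is correlation × 0.62/0.55 (post-vaccination SD 0.62 assumed): 0.338 at correlation 0.3 and 0.564 at 0.5.
- The shift in the adjusted GMT is 10^(0.338 × 0.774) = 1.83-fold and 10^(0.564 × 0.774) = 2.73-fold, the same in both arms. A sixth observed level raises it further.

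**4. Simulation of the adjusted GMT.** The set-up was 96 scenarios of 60 runs: 250 per arm, 20 or 40 centres, centre ICC 0.05, baseline GMT 3 to 60, cut-offs 5, 8 and 14 (within the LLOQ span of SAP Table 5), true ratio 0.9. Shift of CLASS against continuous coding:

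- two-fold titres: 1.16 to 3.27
- whole-number titres: 1.27 to 3.65
- baseline GMT 3 to 6 only: 1.67 to 3.65

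A second set (SD 0.72443, baseline SD 0.6, 20 to 80% low values, correlation 0.2 to 0.5) gave 1.37 to 4.29 for the same two titre types. For unrounded titres with 20% low values it gave 1.11 to 1.36. At baseline GMT 60 with cut-off 5, unrounded titres gave about 1.0. When most titres are unique, equal level weights approach subject weights.

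**5. Precision.** With 500 subjects and 20 centres, the continuous model leaves 500 − 1 − 1 − 19 − 1 = 478 residual degrees of freedom. CLASS coding with L levels leaves 480 − L. The loss is close to √(478/(480 − L)).

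| Titres | L | √(478/(480 − L)) | Simulated CI half-width ratio (second set) |
|---|---|---|---|
| two-fold | 6–9 | 1.004–1.007 | 1.000–1.008 |
| whole-number | 25–106 | 1.025–1.131 | 1.02–1.13 |
| unrounded | 101–401 | 1.123–2.460 | 1.12–2.58 |

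In the first set the SE ratio was 1.00 to 1.01 for two-fold titres. For whole-number titres it was 1.03 to 1.08 at GMT 3 to 6, 1.15 to 1.17 at GMT 20 and 1.33 to 1.40 at GMT 60.

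**6. The ratio itself.** In the 96 scenarios the mean estimate stayed within 5% of the truth, with no consistent direction. Allocation is independent of baseline, so coding baseline as a factor does not bias the contrast.

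**7. Annex model.** If country explains none of the centre variation, replacing centre by country multiplies the SE by at most about 1/√(1 − ICC): 1.010 at an assumed ICC of 0.02 and 1.054 at 0.10. Protocol Table 14 assays each antigen in two groups, so a third group contributes no data.

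**The case against.** The strongest reply is about reach. The ANCOVA only might be run, and harm needs it to be run verbatim and its arm-level LSMEANS reported. The sentence promising adjusted GMTs follows the centre-ANOVA paragraphs, and the ANOVA code, which is correct, already supplies centre-adjusted GMTs. This stands: a reader might infer that the promised tables will be wrong, and the documents do not support that.

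The size also rests on assumed inputs. With two-fold titres the CLASS interval was even narrower than the plain ANOVA's (SE ratio 0.88 to 0.99), so the precision loss depends on a granularity the documents do not give. This stands too, and it is why only ranges are reported. It does not rescue the code, because with two-fold titres the adjusted GMTs are still displaced.

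On the annex, Section 10.1 is generic sponsor text, and Section 5.4.2 names this trial's contrasts and gives the code. Annex 10.1.5.3 itself asks that it be clear whether a model is limited to some groups. Reading 5.4.2 as governing is natural, but it is not written down, so an alignment edit remains worthwhile.

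**Conclusion.** The CLASS statement is wrong as written, and the consequence is minor. If the optional ANCOVA is run as coded, adjusted GMTs in both arms are roughly 1.2 to 3.6 times too high with two-fold or whole-number titres, under the assumptions in steps 2 and 4 (first set). The ratio keeps its target but can lose precision: negligibly with two-fold titres, by up to about 1.4 times in SE with whole-number titres, and by 2 times or more with unrounded titres at higher baselines.

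Stronger readings that the documents do not support:

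- **That a non-inferiority decision or the 90.23% power is at risk.** Both rest on models without baseline, and the centre ANOVA code is correct. In the widest unrounded cases the simulated chance of the ANCOVA's lower limit exceeding 0.5 fell to 0.42 to 0.47 (40 runs per scenario), but that limit decides nothing.
- **That the GMT shift occurs at any titre resolution.** It can vanish when titres are fine and few lie below the cut-off.
- **That the annex conflict moves the GMC lower limit by a stated amount.** The SDs in Protocol Table 19 read as total SDs and come from ELISA, which SAP Section 8 replaces with ECL. Only a small SE effect, up to about 5% at an assumed ICC of 0.10, can be claimed.

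**What to change.** In the ANCOVA code use `class trt center;` and keep `model Ab_post = trt center Ab_pre;`, so that LSMEANS is evaluated at the mean log10 baseline. Correct the prose that calls baseline a factor. Limit the ANCOVA to hSBA, because Protocol Table 14 plans no Visit 1 ELISA read-out, and hence no baseline for the ECL assay that replaces it.

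As a secondary edit, delete annex 10.1.5.3 or align it with Section 5.4.2: centre (the minimisation factor in Protocol Section 7.2.2.2.1), two groups per endpoint, and country only as the stated fallback.

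The cost is one word of SAS code and a few SAP sentences. No new data are needed.
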